### **8.5.3. Interim Analysis**

No interim analysis is planned.

### **8.5.4. Safety Analysis**

All subjects entered into the study and randomized will have detailed information collected on adverse events starting at enrollment and for the duration of follow-up, as described elsewhere. The primary safety endpoints of frequency of AEs, SAEs, and AESIs will be described.

### **8.5.5. Exploratory Analyses**

To characterize (1) the baseline gut bacterial community composition and host immune phenotype associated with S/SC/F-CDI, we will apply 16S ribosomal RNA (rRNA) gene sequencing to initial (pre-FMT) stool specimens, Luminex bead assay (cytokine/chemokine levels) and flow cytometric analysis (granulocyte/mononuclear cell counts) to serum and blood specimens collected as part of routine clinical care prior to FMT. To characterize (2) the change in gut bacterial community composition and host immune phenotype associated with each of the above treatment strategies, we will apply the same assays to post-FMT stool, peri-rectal, and serum/blood specimens. To determine (3) the relationship between baseline gut bacterial community composition, host immune phenotype, and treatment outcome in patients with S/SC/F-CDI, we will perform regression modeling with bacterial community composition, cytokine/chemokine levels, and granulocyte/mononuclear cell counts as predictor variables.

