To address the exploratory aims, daily swabs of available stool and peri-rectal swabs will be taken for microbiome analysis for 7 days post-FMT or post-enrollment for non-PMT arm. If blood that was collected for clinical purposes would otherwise be discarded, it will be captured for immune response phenotyping. Stool specimens will be obtained by placing flocced nylon swabs in stool if available (e.g. in bag of fecal management system). In addition, peri-rectal swabs will be obtained if possible. Blood will be collected from residual material available in EDTA ("purple top") vacutainer tubes already collected in the clinical laboratory. If subjects have been discharged from the hospital, no swabs will be collected. If no residual blood is available, or if subjects have been discharged from the hospital, no blood will be collected. Stool, peri-rectal and blood specimen analysis will be directed by the principal investigator and study team.

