**Table 3: Schedule of study procedures**

Study Phase	Screening & Enrollment	Intervention	Follow-Up: 30 & 60 minutes	Follow-Up: First 3 Days	Follow-Up: 7 days	Follow-Up: 30 days	Follow-Up: 90 days	Follow-Up: 180 days
Study Days	1	1* (Retreatment Day 4 / 7*)	1* (Retreatment Day 4 / 7*)	Final Intervention +1, +2, +3	Final Intervention +7	Final Intervention +30	Final Intervention +90	Final Intervention +180
Surveillance Test Review	X							
Medical Record Review	X			X	X	X	X	X
Review Inclusion/Exclusion	X							
Informed Consent	X							
Enteral Access Check	X							
Randomization	X							
Dispense PMT to Clinical Site		X						
PMT Receipt Check		X						
PMT Administration		X						
Compliance Check		X						
Vital Signs Review			X	X	X			
Symptom Review			X	X	X	X	X	X
Laboratory Review				X	X	X	X	X
CRF3 / Outcomes Check				X	X	X	X	X
Adverse Event Check		X	X	X	X	X	X	X
Microbiome Swab from Otherwise Discarded Stool				X	X			
Immune Phenotypic Analysis on Otherwise Discarded Whole Blood				X	X			

\*If PMT administration is unable to be performed on days 1, 4 and/or 7, administration and 30/60-minute follow up within 1 calendar day before or after those days will be permitted (for the first administration, administration within 1 calendar day after enrollment will be permitted). If the first administration occurs on day 2, then the second and third administration dates (if eligible) will be days 5 and 8 (+/- 1 calendar day).

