### **7.6. Other Evaluations, Measures**

Subjects will be provided with a diary and thermometer to keep track of their temperature (once a day), stool frequency, and any emesis. This diary will be reviewed with subjects at their 7-day follow-up visit.

For the exploratory aim, stool microbiome analysis will be performed on stool samples and peri-rectal swabs. Likewise, immune phenotypic analysis using flow cytometry may be performed on a subset of subjects using whole blood collected for clinical purposes, which would otherwise be discarded. Stool specimens will be obtained by placing flocced nylon swabs in available stool. Peri-rectal swabs will be obtained if possible. Blood will be collected from residual material available in EDTA ("purple top") vacutainer tubes already collected in the clinical laboratory.

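### Section 8.5.5 analyses pre-FMT stool and blood, but no procedure or Table 3 entry collects either before the first dose; the gap is clearest for stool in the two FMT arms.

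*Combined protocol and SAP*

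**What the plan says.** **Analysis.** Section 8.5.5 assigns 16S "gene sequencing to initial (pre-FMT) stool specimens" to the baseline objective. Cytokine and flow-cytometry assays use "serum and blood specimens collected as part of routine clinical care prior to FMT". For the change objective, "we will apply the same assays to post-FMT stool, peri-rectal, and serum/blood specimens". For the third objective, outcome is regressed on the microbiome and immune measures; Section 2.3 makes clear that the baseline values are meant.

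**Collection.** Section 6.3.1, which sits in the follow-up phase, states that "daily swabs of available stool and peri-rectal swabs will be taken for microbiome analysis for 7 days post-FMT or post-enrollment for non-PMT arm". On blood it says: "If blood that was collected for clinical purposes would otherwise be discarded, it will be captured for immune response phenotyping". Section 7.6 adds "Blood will be collected from residual material available in EDTA" tubes already in the clinical laboratory. It describes how specimens are obtained but not when.

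**Schedule.** Table 3 has two specimen rows, "Microbiome Swab from Otherwise Discarded Stool" and "Immune Phenotypic Analysis on Otherwise Discarded Whole Blood". Each is marked under First 3 Days and 7 days and nowhere else. Those columns count days from the final intervention.

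**The concern.** All three exploratory objectives refer to baseline: the first describes it, the second measures change from it, and the third uses it as a predictor. The collection text and the schedule begin only once dosing or enrollment has happened. Staff who follow them exactly would take no stool from an FMT-arm subject until donor material is already present. Enrollment and the first dose share Day 1, with one calendar day of slack, so the pre-dose window is short and a missed stool specimen cannot be replaced by later sampling.

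The gap also differs by arm. An early control specimen follows no FMT, whereas an early FMT-arm specimen does. An analyst who filled the gap with each subject's first specimen would be comparing two different things under one label.

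**Working it through.** No sample-size, power or error-rate figure bears on this point. The check sets requirement against provision.

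**1. Provision in Table 3, by column.**

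| Column | Stool swab row | Blood row |
|---|---|---|
| Screening & Enrollment | none | none |
| Intervention | none | none |
| 30 & 60 minutes | none | none |
| First 3 Days | X | X |
| 7 days | X | X |
| 30, 90, 180 days | none | none |

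Rows with a mark before or at the first dose: 0 of 2.

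**2. Provision in the text.** Sections 6.1.1 to 6.1.5 cover test review, record review, consent, the enteral access check and randomization. Sections 6.2.1 to 6.2.4 cover product receipt, administration and monitoring. Neither group contains a research swab or blood capture. Section 4.1 implies that a diagnostic stool existed within the 7 days before enrollment, but nothing says that any of it is kept or sequenced. Under Section 3.1.1, a transferred patient needs only a record of the outside result, so that stool may not be at the site.

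**3. Number of subjects.** Section 4.5 plans 30 per arm, so the two FMT arms hold 2 × 30 = 60. The 2:1 allocation in Section 3.1.6 gives the same total: 90 × 2/3 = 60. Controls number 90 − 60 = 30. How the 60 divide between upper and lower routes does not matter here.

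**4. First tabulated specimen in an FMT subject first dosed on Day 1.** Table 3 gives nominal retreatment on Days 4 and 7, and its first specimen falls on the final intervention +1:

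- one dose: Day 1 + 1 = Day 2
- two doses: Day 4 + 1 = Day 5
- three doses: Day 7 + 1 = Day 8

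The first tabulated specimen can therefore follow up to three doses. The swab sentence in Section 6.3.1 does not itself say final dose, so it could be read as starting after an earlier one. On either reading the specimen is post-dose.

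**5. Stool and blood separately.**

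- *Stool.* The only timed procedure is post-FMT or post-enrollment. No pre-FMT source is named beyond the wording in 8.5.5.
- *Blood.* Section 8.5.5 names routine-care specimens before FMT. The blood sentence in Section 6.3.1 carries no time window of its own; the 7-day limit belongs to the swab sentence. What is missing is a procedure or schedule entry that captures pre-dose tubes. The sources also disagree on material: 8.5.5 refers to serum, while Sections 6.3.1 and 7.6 provide residual EDTA tubes, which yield whole blood or plasma.

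**6. Consequence for each objective, using scheduled samples only.**

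- *Objective 1:* control specimens approximate baseline, though they come after enrollment and on antibiotics. The FMT arms contribute no pre-dose stool.
- *Objective 2:* within-subject change in stool composition is unavailable in the FMT arms.
- *Objective 3:* a first-specimen substitute would put treatment effect into a predictor labelled baseline for the 60 FMT subjects but not for the 30 controls.

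**The case against.** The strongest reply is that Section 8.5.5 already intends pre-FMT specimens, so the schedule merely fails to repeat the intention. Blood needs no study draw, Section 7.6 puts no time limit on swabs, and a diagnostic stool exists before enrollment. Much of this stands for blood: the material will often exist, and the defect is a missing instruction. It is weaker for stool. A statement of what will be assayed does not tell staff to collect it, and the one instruction with a timing points to the period after dosing.

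A reader might infer that the baseline and change objectives cannot be estimated at all. The documents do not support that. Objective 1 is not arm-specific, so controls can inform it. Objective 3 could be explored in the same controls. Post-treatment composition can be compared between randomized arms without a baseline.

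A reader might also infer that all 60 FMT subjects lose both stool and blood. That is too strong as well. Not scheduled is not the same as not obtainable, pre-FMT blood has a named source, and Sections 7.6 and 7.8 say immune phenotyping may be done on only a subset, so 60 is not the denominator for blood.

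**Conclusion.** The analysis plan and the collection schedule conflict, and the conflict should be resolved. Scheduled pre-FMT specimens number zero in both specimen rows. The consequence is clearest for stool in the FMT arms, planned at 60 of 90 subjects: their baseline composition and within-subject change would depend on a source that the protocol does not specify. For blood the finding is limited to the absence of a capture step and the serum/EDTA mismatch.

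This rests on two assumptions: staff follow the written schedule, and enrollment reaches the planned allocation. The figure of 60 counts subjects without a scheduled pre-dose stool specimen; it does not forecast how many would end up with none. Stool and peri-rectal collection is conditional on availability throughout, so some subjects would lack a baseline specimen even under a corrected schedule.

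The effect is confined to the exploratory objectives. The primary and secondary endpoints, the power calculation and the safety analysis do not use these specimens.

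**What to change.** 1. **Table 3:** add a mark to both specimen rows for collection after consent and before the first dose (at randomization for controls).
2. **Sections 6.3.1 and 7.6:** add matching text for one stool or peri-rectal swab and capture of residual clinical EDTA blood at that point.
3. **Baseline window:** define how long before the first dose, or before randomization in controls, a specimen may be taken and still count as baseline. The documents give no figure, so the sponsor must choose one.
4. **Diagnostic stool:** state whether residual stool from the qualifying test may substitute, and what happens for transferred patients whose specimen is elsewhere.
5. **Section 8.5.5:** make the serum wording match the EDTA material collected, and allow a peri-rectal swab at baseline, since the current text names only stool there. Say how subjects without a baseline specimen are handled, and rule out using a post-dose specimen as baseline.

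The cost is one extra swab per subject and a small amount of staff effort at enrollment. The swab method and the residual-blood source are already in the plan, and no extra blood draw is needed.

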## **8.6. *Subject Population(s) for Analysis***

For the primary analysis, a modified intention-to-treat (mITT) population will be used, in which subjects who die following randomization but before receiving their first FMT will be excluded. Secondary intention-to-treat and per-protocol analyses will also be performed. All randomized subjects will be included in the latter analyses.

## **9. Safety and Adverse Events**

### **9.1. *Definitions***

#### **9.1.1. Adverse Event**

An adverse event (AE) is any untoward medical occurrence associated with the use of a drug in humans, whether or not considered drug related. Intercurrent illnesses or injuries should be regarded as adverse events.

A pre-existing condition should be recorded as an adverse event if the frequency, intensity or the character of the condition changes.

### 9.1.2. Serious Adverse Event

Adverse events are classified as serious or non-serious. A serious adverse event (SAE) is any AE that, in the view of either the investigator or the sponsor, is:

- fatal
- life-threatening
- requires or prolongs hospital stay
- results in persistent or significant disability or incapacity
- a congenital anomaly or birth defect
- an important medical event

Important medical events are those that may not be immediately life threatening, but are clearly of major clinical significance. They may jeopardize the subject, and may require intervention to prevent one of the other serious outcomes noted above. For example, drug overdose or abuse, a seizure that did not result in in-patient hospitalization, or intensive treatment of bronchospasm in an emergency department would typically be considered serious.

### 9.1.3. Adverse Events of Special Interest (AESI)

Based on prior published experience with FMT-associated risks (Table 1), we have defined several adverse events of special interest.

In the initial, 60-minute bedside observation period following administration of investigational product, subjects will be monitored with close attention to the following:

- allergic reaction (temperature, skin rash, heart rate, or blood pressure change as already described) -- PMT-001, 002, and 003
- sepsis or shock (temperature, heart rate, or blood pressure change as already described) – PMT-001, 002, and 003
- bowel injury (abdominal pain change as already described) – PMT-001, 002, and 003
- aspiration (respiratory rate or oxygen saturation change as already described) – PMT-002 and 003 only

In the subsequent, 7-day monitoring period following administration of investigational product, subjects will be monitored with close attention to the following:

- donor-derived infection (temperature or abdominal pain change as already described) – PMT-001, 002, and 003
- worsening CDI (temperature, change in stool frequency/quantity or abdominal pain, or emesis as already described) – PMT-001, 002, and 003

In the subsequent, 30-, 90-, and 180-day monitoring periods, subjects will be monitored with close attention to the following:

- transmitted infection (temperature or abdominal pain change as already described) – PMT-001, 002, and 003
- recurrent CDI (temperature, change in stool frequency/quantity or abdominal pain, or emesis as already described) – PMT-001, 002, and 003
- metabolic changes (polydipsia, polyuria, weight gain, or weight loss) – PMT-001, 002, and 003

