#### 3.2.3. Primary Safety Endpoints

The primary safety endpoints will include:

- Frequency of solicited adverse events (AEs)
- Frequency of serious adverse events (SAEs)
- Frequency of AEs of special interest (AESIs)

See [Section 9](#) for additional details on adverse event definitions.

Monitoring post-PMT administration will occur in three phases:

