### ***12.2. Benefits***

Potential direct benefits include: cure or improvement of CDI symptoms more quickly than with standard of care, reduction in risk of complications of CDI (death, need for surgery), reduction in risk of recurrence of CDI, which have been suggested by observational studies to date (Table 1). Indirect benefits include contributing to medical knowledge about the utility of FMT in this study population and therefore helping patients who have this disease in the future.

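### Worsening CDI, recurrent CDI and metabolic change are written as PMT-tagged AESIs with no post-enrollment equivalent, so this primary safety endpoint has no pre-specified control rate

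*Combined protocol and SAP*

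**What the plan says.** Section 3.2.3 lists "Frequency of AEs of special interest (AESIs") as a primary safety endpoint, beside solicited AEs and SAEs. Section 8.5.4 says these frequencies will be described. It names no arm, denominator or comparison for AESIs.

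Section 9.1.3 explains how the AESIs were chosen: "Based on prior published experience with FMT-associated risks (Table 1), we have defined several adverse events of special interest". It then sets three windows:

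- **Bedside.** "In the initial, 60-minute bedside observation period following administration of investigational product, subjects will be monitored with close attention to the following": allergic reaction, sepsis or shock, bowel injury, aspiration.
- **Seven days.** "In the subsequent, 7-day monitoring period following administration of investigational product, subjects will be monitored with close attention to the following": donor-derived infection, worsening CDI.
- **Later follow-up.** "In the subsequent, 30-, 90-, and 180-day monitoring periods, subjects will be monitored with close attention to the following": transmitted infection, recurrent CDI, metabolic changes.

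Every item in all three lists ends with a product tag. Aspiration is limited to PMT-002 and PMT-003; all other items carry all three products.

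Section 8.5.4 also says: "All subjects entered into the study and randomized will have detailed information collected on adverse events starting at enrollment and for the duration of follow-up". Section 12.2 names "reduction in risk of recurrence of CDI" among the potential direct benefits.

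**The concern.** Worsening and recurrent CDI are part of the disease. Section 1.1 itself names recurrence and progression to severe disease as key challenges of CDI, so controls will have these events too. A special-interest rate for FMT subjects alone mixes background disease with any product effect, and the reader cannot separate the two.

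Recurrence is the sharper case because it is both a possible harm and a claimed potential benefit. If its only definition as an outcome applies to one side of the randomization, a trial with 180 days of follow-up ends without a planned between-arm result for it. If a control definition is supplied after the data have accumulated, it will be chosen by people who know the assignments, because Section 5.6 states that neither subjects nor investigators are blinded.

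**Working it through.** The documents state no AESI rate, margin or power, so there is no planned figure to reproduce. The check compares the text across sections, then works out the time origin and the precision available.

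**1. Does Section 9.1.3 cover controls?**

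| AESI | Window wording in 9.1.3 | Tag | Related data in controls |
|---|---|---|---|
| Worsening CDI | 7 days, tied to product administration | PMT-001, 002, 003 | Worsened diarrhea and fever, days 1–3 (3.2.3.2); temperature, stools and emesis for 7 days (3.1.5, 6.3.1) |
| Recurrent CDI | 30, 90, 180 days; refers to subjects only | PMT-001, 002, 003 | Interviews and record review at 30, 90 and 180 days (6.3.2–6.3.4, 7.1) |
| Metabolic changes | 30, 90, 180 days; refers to subjects only | PMT-001, 002, 003 | New metabolic disease at 30, 90 and 180 days (3.2.3.3) |

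The aspiration tag shows that the tags say to whom an item applies. Where the protocol means to include controls, it adds a post-enrollment alternative: Sections 3.1.5, 3.2.3.2, 3.2.3.3 and 6.3.1–6.3.4 all do so. Section 9.1.3 does not. Section 9.1.4 has the same gap: its 50% symptom threshold is measured against the 48 hours around the intervention, which controls do not have.

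**2. Denominator.** Section 4.5 targets 30 per arm. On the literal reading, 30 + 30 = 60 FMT subjects are covered and 30 of 90 subjects are not.

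**3. Is recurrence an endpoint elsewhere?** It is not in the primary endpoint (3.2.1), the secondary endpoints (3.2.2, 8.2) or the follow-up safety endpoints (3.2.3.3). The AESI entry, "recurrent CDI (temperature, change in stool frequency/quantity or abdominal pain, or emesis as already described"), is its only appearance as a defined outcome. Readmission within 60 days of discharge is related but not specific to CDI.

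**4. Time origin.** Follow-up runs from the final FMT in PMT subjects and from enrollment in controls. By the footnote to Table 3, a first dose on study day 2 puts a third dose on day 8, plus or minus 1, so day 9 at the latest.

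- Difference in clock: 9 − 1 = up to 8 days.
- Seven days after enrollment is study day 8, before a day-9 dose. The post-dose safety window therefore cannot simply be moved to enrollment.
- Thirty days after enrollment is study day 31, which leaves 31 − 9 = 22 days after the latest dose. At 180 days (study day 181) it leaves 172 days.

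A by-arm count from enrollment to day 30 and day 180 therefore works alongside the post-dose windows.

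**5. Precision if the definition covers both groups.** With a common rate p, the 95% half-width for the difference is 1.96 × √[p(1 − p)(1/60 + 1/30)], and 1/60 + 1/30 = 0.05. The rates are assumed.

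- p = 10%: 1.96 × √(0.09 × 0.05) = 0.131
- p = 20%: 1.96 × √(0.16 × 0.05) = 0.175
- p = 30%: 1.96 × √(0.21 × 0.05) = 0.201

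For scale, two-sided 5% power (normal approximation, pooled variance under the null), control rate first: 0.57 for 10% v 30%, 0.47 for 20% v 40%, 0.81 for 20% v 50%. For a reduction from 30% to 10%, the pooled rate is (9 + 6)/90 = 0.167. Then z = [0.20 − 1.96 × √(0.167 × 0.833 × 0.05)] / √(0.21/30 + 0.09/60) = (0.200 − 0.163)/0.092 ≈ 0.40, so power is about 0.65.

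**The case against.** A reader might infer that controls can never have an AESI, that the AESI table must show an FMT rate against zero of 30, and that FMT effects on these events cannot be judged. The documents do not support that reading, for four reasons.

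- The sentence for 30, 90 and 180 days is not tied to administration, so for recurrent CDI and metabolic change the restriction rests on the tags alone.
- Section 7.1 schedules record review to day 180, cites Section 9.1.3 by number and sets no arm limit.
- Section 8.5.4 collects adverse events in everyone randomized, Section 3.2.3.3 lists metabolic disease under a heading that includes post-enrollment follow-up, and Section 9.2 records events as diagnoses where possible. Recurrent CDI in a control can therefore be recorded.
- No test of AESIs is planned. A p-value computed against zero of 30 would assume both the recurrence rate and the conclusion.

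It is also fair that some AESIs belong to FMT alone. Bedside reactions and donor-derived or transmitted infection have no meaningful counterpart in subjects given no product. Lower recurrence in Section 12.2 is a potential benefit suggested by observational studies and is not a stated hypothesis of this trial.

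All of this limits the point without removing it. The data exist, but the definition that would turn them into a control rate does not. Two analysts could follow the text and produce different tables for a primary safety endpoint.

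**Conclusion.** The point holds as a gap in definition and reporting. The underlying data are largely collected. Section 9.1.3 ties worsening CDI to product administration and tags worsening CDI, recurrent CDI and metabolic change to PMT, with no post-enrollment equivalent. Read literally, the endpoint gives a rate in about 60 FMT subjects without a background rate from the 30 controls, and recurrent CDI has no pre-specified between-arm result. Control rates could be derived, but under a definition chosen later in an open-label trial.

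This rests on reading the product tags as saying to whom each item applies. If they only separate formulations, the recurrent CDI and metabolic items become ambiguous instead of restricted. The administration-based window for worsening CDI does not depend on the tags. The text should be amended on either reading. The half-widths of 13 to 20 points depend on assumed rates and on 60 v 30 being enrolled; they show that the comparison would be descriptive and would detect only large differences.

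**What to change.** 1. In Section 9.1.3, state that worsening CDI, recurrent CDI and metabolic change apply to all randomized subjects, using the post-PMT or post-enrollment form found elsewhere in the protocol.
2. In Section 8.5.4, report these three by arm with confidence intervals. Count the by-arm comparison from enrollment over a common period, for example to day 30 and to day 180.
3. Keep the existing post-dose windows for product safety.
4. Keep the 60-minute bedside AESIs and donor-derived or transmitted infection as FMT-only, reported without comparison.

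**Cost.** This is a small amount of wording and analysis work, using contacts and record reviews already scheduled. Abdominal pain is a component of the CDI items but is not among the items in the 7-day diary or inpatient record, so it needs one added item or must come from the AE interview. Precision stays limited at 60 v 30, and the report should say so.

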#### 1.1. Background and Relevant Literature

As recently as 2015, the Centers for Disease Control and Prevention (CDC) identified *Clostridium difficile* infection (CDI) as an “urgent” threat associated with upwards of 500,000 infections in the United States each year and resulting in over 15,000 deaths. CDI is characterized by a clinical syndrome that typically includes loose, frequent bowel movements and abdominal pain, which occur as a result of toxin production by colonic *C. difficile*. CDI occurs in patients colonized with toxigenic *C. difficile* and in patients who have newly acquired *C. difficile*. Estimates of the relative contributions of persistent colonization and new acquisition to incident CDI vary. In both cases, the pathogenesis of CDI involves depletion of non-*C. difficile* colonic microbiota, altered bile acid metabolism, germination of (resident or recently ingested) *C. difficile* spores, expansion of a population of vegetative *C. difficile*, toxin production, and colonic inflammation. Key challenges associated with CDI include its recurrence after appropriate antibiotic treatment (R-CDI), and its progression to a more severe disease state with systemic signs of inflammation or even sepsis. The latter, termed severe or severe-complicated/fulminant CDI (S/SC/F-CDI), often requires extended hospitalizations, may require colectomy, and is associated with high rates of mortality (Kelly BJ 2018). At present, antibiotic treatment is the recommended therapy for early R-CDI, and antibiotic treatment followed by FMT is the recommended therapy for later R-CDI. Antibiotics alone are the recommended therapy for S/SC/F-CDI (McDonald 2018), but observational studies suggest a benefit for FMT in the S/SC/F-CDI population as well (Weingarden 2013; Agarwal 2015; Aroniadis 2015; Fischer 2015; Fischer 2017).

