### **3.1.3. Post-PMT Administration monitoring: Bedside for 60 Minutes**

Subjects will be monitored at 30 and 60 minutes following completion of PMT administration. Subjects will be visually observed for signs of aspiration or other respiratory distress (PMT-002 and PMT-003), abdominal pain, vomiting, other signs of allergic reaction, and changes in vital signs (PMT-001, PMT-002, and PMT-003). Vital signs (temperature, heart rate, respiratory rate, blood pressure, and oxygen saturation) will be checked. The following vital sign changes will be recorded if observed, and will prompt notification of the primary clinical care team: (1) heart rate increase or decrease by greater than or equal to 30 beats per minute; (2) respiratory rate increase or decrease by greater than or equal to 10 breaths per minute or if respiratory rate drops below 10 or increases above 25 (if respiratory rate not already outside these ranges); (3) temperature:

increase or decrease by greater than or equal to 2 degrees Fahrenheit, or if temperature drops below 96°F or increases above 100.4°F (if temperature not already outside these ranges); (4) oxygen saturation decrease by greater than or equal to 5% (sustained for more than 20 seconds) or if oxygen saturation drops below 90% (on current amount of oxygen delivered, sustained for more than 20 seconds); (5) blood pressure decrease by more than 30 mmHg systolic or 15 mmHg diastolic, or if blood pressure drops below 90/60 (if blood pressure not already outside these ranges).

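### The donor-derived and transmitted infection AESIs rest only on temperature or abdominal pain change, signs shared with CDI, with no stated rule for telling the two apart and no control-arm count

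*Combined protocol and SAP*

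**What the plan says.** Section 3.2.3 makes "Frequency of AEs of special interest (AESIs") one of the primary safety endpoints and sends the reader to Section 9 for definitions. Section 9.1.3, under the Definitions heading, gives two pairs of follow-up AESIs:

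- For the 7-day period: "donor-derived infection (temperature or abdominal pain change as already described") and "worsening CDI (temperature, change in stool frequency/quantity or abdominal pain, or emesis as already described").
- For the 30-, 90- and 180-day periods: "transmitted infection (temperature or abdominal pain change as already described") and "recurrent CDI (temperature, change in stool frequency/quantity or abdominal pain, or emesis as already described").

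The 60-minute and 7-day periods are timed from administration of the product, and every item, in all periods, is labelled with PMT product numbers. Section 9.1.3 mentions no culture, *C. difficile* test, other pathogen result, donor link or adjudication.

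Elsewhere, 9.2 asks for each adverse event to be recorded as a diagnosis where possible and assessed for relatedness. Sections 7.1 and 7.4 and Table 3 have the medical record and care-team laboratory values reviewed at every follow-up. Section 8.5.4 collects adverse events in all randomized subjects and describes the AESI frequencies without naming a comparison between arms.

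**The concern.** The signs that define a product-attributed infection are signs the disease produces, and all of them also belong to the paired CDI category. A reader of the final AESI table could not tell whether a donor-derived infection entry reflects a pathogen from the product, CDI that has not yet settled, or an unblinded investigator's choice between two labels (Section 5.6 confirms that nobody is blinded). With no AESI frequency defined for standard of care, there is also no background count to set beside it.

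This matters because safety is the secondary objective, the PMT products have no prior clinical data (1.2.2), and donor-derived infection is among the most severe risks listed in 12.1. Recurrence is affected too. Section 12.2 counts "reduction in risk of recurrence of CDI, which have been suggested by observational studies to date" among the potential benefits, yet recurrence is recorded only as this sign-based AESI labelled for the PMT products.

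**Working it through.** The plan states no AESI rate and no safety power, so there is no figure to reproduce. The check is textual, followed by an illustration.

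**1. Sign lists in 9.1.3**

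| Window | Infection AESI | Paired CDI AESI | Only in the CDI list |
|---|---|---|---|
| 7 days | temperature, abdominal pain | temperature, stool, abdominal pain, emesis | stool, emesis |
| 30, 90, 180 days | temperature, abdominal pain | temperature, stool, abdominal pain, emesis | stool, emesis |

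In both windows the infection list is a strict subset of the CDI list. On the listed signs, any event that fits the infection item also fits the CDI item, and no sign is specific to infection.

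**2. Does CDI produce these signs?** Section 1.1 describes CDI as typically including "loose, frequent bowel movements and abdominal pain, which occur as a result of toxin production by colonic" *C. difficile*. Section 4.1 and Table 2 use a single temperature of at least 38.5 °C or below 35.6 °C as a severity criterion. Section 9.1.4 expects fever and abdominal pain from both the disease and the product.

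**3. Do the references to earlier text settle it?** For temperature, 3.1.3 has "increase or decrease by greater than or equal to 2 degrees Fahrenheit, or if temperature drops below 96°F or increases above 100.4°F". That rule was written for the 60-minute bedside window, and its range limits apply only if the temperature was not already outside them.
- 100.4 °F = (100.4 − 32) × 5/9 = 38.0 °C. Section 3.2.3.2, however, sends adverse event definitions to 3.2.1, where the temperature limit is 38.5 °C (with a separate SIRS limit of 38 °C).
- If the bedside rule were carried into follow-up, the 2 °F clause works in both directions. A subject at 38.5 °C (38.5 × 9/5 + 32 = 101.3 °F) who cools to 99.3 °F would meet it by improving.
- Neither section defines a change in abdominal pain, and pain is not among the items recorded daily for 7 days in 6.3.1.

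**4. Does 9.1.4 separate the causes?** Its threshold is a 50% rise in gastrointestinal symptom severity. The examples are stools, diarrhea volume, vomiting and nausea, not temperature or pain. Worsening CDI would cross it as readily as a product effect.

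**5. Illustrative size.** Section 4.5 gives 30 subjects per arm, so 60 PMT and 30 control. Let q be the assumed share of subjects in whom CDI alone produces a qualifying sign, with one flag per subject.
- Expected PMT subjects with signs and no donor infection = 60q: 3 at 5%, 9 at 15%, 30 at 50%.
- Chance of at least one = 1 − (1 − q)^60. At q = 5% this is 1 − 0.95^60 = 0.954.
- Expected controls with the same signs = 30q: 1.5, 4.5 and 15.

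**6. What a control count could show.** For an excess d over q, power = Φ[(d − 1.96 × SE0)/SE1], with SE0 from the pooled and SE1 from the separate proportions, 30 against 60, two-sided 0.05 (my choice of level).
- Example, q = 20% and d = 20 points: pooled proportion (6 + 24)/90 = 0.333; SE0 = √(0.333 × 0.667 × (1/30 + 1/60)) = 0.105; SE1 = √(0.16/30 + 0.24/60) = 0.097; power 0.47.
- Across q from 5% to 50%: 0.15 to 0.25 for a 10-point excess, 0.44 to 0.67 for 20 points, 0.78 to 0.93 for 30 points.

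Control counts would therefore give a background rate but would detect only a large excess.

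**The case against.** The strongest reply is that 9.1.3 tells staff which signs to watch and does not score them. A reader might infer that the natural course of CDI is automatically counted as donor-derived infection, that each event is counted twice, and that the safety objective cannot separate the two. The documents do not support any of these as stated:

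- No section says that a sign alone makes an event. Section 9.2 records a diagnosis where possible, so a fever diagnosed as CDI can be entered as CDI.
- Record review under 7.1, which cites 9.1.3, and laboratory values under 7.4 bring care-team cultures and *C. difficile* tests into view.
- Bacteremia is a separate secondary endpoint and safety parameter, and adverse events are collected in the control arm.
- The halting provision in 9.4 requires an infection judged related to the product, which the sign list does not decide.
- Recurrence is named as a potential benefit, not as an objective or endpoint, so its absence from the secondary endpoints is not an error.
- The separate safety monitoring plan and DSMB Charter may contain classification rules.

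All of this stands against the stronger readings. It does not supply what is missing. Section 9.1.3 says the AESIs are defined there, and 3.2.3 relies on that. The safeguards allow separation by judgment but give no criterion for it. Bacteremia is followed only to day 30 and would miss infection outside the bloodstream. Collecting adverse events in all arms does not define an AESI frequency for controls.

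**Conclusion.** The point holds in a limited form. The infection AESIs are non-specific as written: their signs lie wholly within the paired CDI lists and are produced by CDI itself. Separation is possible but rests on unblinded judgment without a stated criterion. One event can enter both categories, since nothing requires or forbids it, and no control-arm AESI frequency is defined.

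The nesting follows from the text and needs no assumption. The size does. The 9 to 30 subjects come from an assumed background rate of 15% to 50%, one flag per subject, and a reading in which the signs alone are enough. They are not figures from the documents and do not forecast what would be reported. This is a worthwhile clarification of a primary safety endpoint and does not affect the efficacy analysis.

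**What to change.** In 9.1.3, state that the listed signs trigger review, and classify each event from results already in the medical record:

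- (a) CDI worsening or recurrence, with recurrence requiring return of diarrhea after resolution plus a positive *C. difficile* test;
- (b) confirmed non-*C. difficile* infection, meaning a pathogen has been identified. Possible donor origin is recorded separately through the 9.2 relatedness assessment and is not presumed from timing after a dose;
- (c) unclassified fever or abdominal pain.

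Allow (a) and (b) together when both are confirmed, and state how such an event is counted. Apply the categories from enrollment in all three arms and tabulate them by arm in 8.5.4. Include test-confirmed recurrence to days 90 and 180 as a descriptive outcome. Given the power shown above, the table should be read as description, not as a test.

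The cost is amendment wording, CRF categories and one table shell. No tests are added, because only care-team results are used. The downside is that events never tested stay in (c), so some true infections or recurrences will not be labelled, although they are still reported as adverse events.
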